5.4.3.2.1 Laboratory values over time

Chemistry, hematology and quantitative urinalysis (observed value, absolute change from Baseline) will be summarized in standard units using descriptive statistics at each scheduled visit. Qualitative urinalysis results will be summarized in frequency tables for each visit.

The central data will be used for the summary tables. If multiple central lab data were captured at scheduled visits, the average would be used for continuous values, or the worst will be used for categorical values.

Measurements Below the Limit of Quantification (BLQ) will be imputed with half of the lower limit of quantification Lower Limit of Quantification (LLOQ), and measurements Above the Limit of Quantification (ALQ) will be imputed to the upper quantification limit for the purpose of quantitative summaries.

All laboratory test results will be listed, including Baseline, scheduled and unscheduled visits with results in standard unit. Values outside the reference range for the continuous variables will be flagged in the listings. The reference ranges will also be reported in the listings. Additional lab test, including pregnancy testing, will also be listed.

5.4.3.2.2 Individual Subject Changes of Laboratory Values

The laboratory variables that are categorized as normal, high or low based on the reference range supplied by the analytical laboratory will be presented in shift tables from Baseline to each scheduled post-Baseline visit and any post-Baseline visit (including unscheduled visits).

5.4.3.2.3 Laboratory Marked abnormalities

Treatment-emergent marked abnormalities (TEMAs) in laboratory parameters will be summarized at each scheduled visit and at any visit (including unscheduled visit). Thresholds for defining marked abnormalities for relevant laboratory parameters are available in Appendix 6.2. Treatment-emergent is defined as meeting the MA criteria at any post-Baseline visit while the MA criteria are not present before dosing.

Listings will include a flag for values identified as TEMA.

5.4.3.2.4 Assessment of potential liver toxicity

To assess the potential for liver toxicities, the following criteria will be used to define levels of liver function tests (LFT) elevation:

- AST: $\geq 3 \times \text{ULN}$, $\geq 5 \times \text{ULN}$, $\geq 8 \times \text{ULN}$, $\geq 10 \times \text{ULN}$, $\geq 20 \times \text{ULN}$
- ALT: $\geq 3 \times \text{ULN}$, $\geq 5 \times \text{ULN}$, $\geq 8 \times \text{ULN}$, $\geq 10 \times \text{ULN}$, $\geq 20 \times \text{ULN}$

- AST or ALT: $\geq 3 \times \text{ULN}$, $\geq 5 \times \text{ULN}$, $\geq 8 \times \text{ULN}$, $\geq 10 \times \text{ULN}$, $\geq 20 \times \text{ULN}$
- Total bilirubin (TBL): $\geq 1.5 \times \text{ULN}$, $\geq 2 \times \text{ULN}$
- ALP: $\geq 1.5 \times \text{ULN}$

Hepatic events will be defined as:

- TEAEs with narrow Standardised MedDRA Queries (SMQ) of “Drug related hepatic disorders - comprehensive search (SMQ)”. However, these 2 sub-SMQs are to be excluded: “Liver neoplasms, benign (incl cysts and polyps) (SMQ)” and “Liver neoplasms, malignant and unspecified (SMQ)”.

The following laboratory criteria for potential drug induced liver injuries are defined as follows:

- AST or ALT $\geq 3 \times \text{ULN}$ with TBL $\geq 1.5 \times \text{ULN}$
- AST or ALT $\geq 3 \times \text{ULN}$ with TBL $\geq 2 \times \text{ULN}$
- AST or ALT $\geq 3 \times \text{ULN}$ with INR > 1.5 (if INR is measured)

In addition, post-baseline potential Hy’s Law cases will be identified using the following definition:

- either AST or ALT $\geq 3 \times \text{ULN}$ with concurrent ALP $< 2 \times \text{ULN}$ and concurrent total bilirubin $\geq 2 \times \text{ULN}$

In order to meet the above criteria, a study participant must experience the elevation in Bilirubin and ALT and AST (and the absence of the ALP elevation) at the same date. For example, a study participant who experiences a $> 2 \times \text{ULN}$ elevation of bilirubin at one date and a $> 3 \times \text{ULN}$ elevation in ALT (or AST) at a subsequent visit date has not fulfilled the Hy’s law criteria.

The number and percentage of study participants with elevated liver function tests will be presented at any visit (including unscheduled visits) in the SS. The number and percentage of study participants with potential drug induced liver injuries including those who potentially meet the Hy’s law criteria and Drug related hepatic disorders TEAEs will be summarized. The liver function results for study participants with elevated liver function results will be listed.

Scatterplots for each liver function test will be presented to show the shifts from Baseline to the maximum post-Baseline result. The ULN of concern (i.e., $3 \times \text{ULN}$ for ALT or AST, and $2 \times \text{ULN}$ for TBL or ALP) will also be presented as lines on the plots. In addition, a scatterplot of the maximum post-Baseline TBL (/ULN) versus the maximum post-Baseline ALT (/ULN) will be provided on a logscale. Reference lines of 3ULN for ALT and 2ULN for TBL will be presented on the graph. If any study participant meets the potential Hy’s law criteria, a graph displaying each liver function test (expressed as X ULN on a logscale) by time will be presented for each identified case.

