### **8.2.4 Clinical safety laboratory assessments**

See Appendix 2 (Section [10.2](#)) for the list of clinical laboratory tests to be performed and the Schedule of Activities (Section [1.3](#)) for the timing and frequency.

The Investigator must review the laboratory report, document this review, and record any clinically relevant changes occurring during the study in the AE section of the eCRF. The laboratory reports must be filed with the source documents. Clinically significant abnormal laboratory findings are those which are not associated with the underlying disease, unless judged by the Investigator to be more severe than expected for the study participant's condition.

All laboratory tests with values considered clinically significantly abnormal during participation in the study should be repeated until the values return to normal or baseline or are no longer considered clinically significant by the Investigator or Medical Monitor.

If such values do not return to normal/baseline within a period of time judged reasonable by the Investigator, the etiology should be identified, and the Sponsor notified.

All protocol-required laboratory assessments, as defined in Appendix 2 (Section [10.2](#)), must be conducted in accordance with the Laboratory Manual and the Schedule of Activities (Section [1.3](#)).

If laboratory values from nonprotocol specified laboratory assessments performed at the institution's local laboratory require a change in study participant management or are considered clinically significant by the Investigator (eg, SAE or AE or dose modification), then the results must be recorded in the eCRF.

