## 10.2 Appendix 2: Clinical laboratory tests

The tests detailed in the table below will be performed by the central laboratory.

- Local laboratory results are only required in the event that the central laboratory results are not available in time for either study medication administration and/or response evaluation. If a local sample is required, it is important that the sample for central analysis is obtained at the same time. Additionally, if the local laboratory results are used to make either a study medication decision or response evaluation, the results must be entered into the eCRF.
- The use of local laboratory results may be considered, if necessary, after consultation with the appropriate Sponsor representative (eg, Clinical Project Manager or Study Physician).
- Protocol-specific requirements for inclusion or exclusion of study participants are detailed in Section 5.1 and Section 5.2 of the protocol.
- Additional tests may be performed at any time during the study as determined necessary by the Investigator or required by local regulations.

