**Table 10-3: Liver chemistry stopping criteria and follow-up assessments**

Liver chemistry stopping criteria	
ALT-absolute	ALT $\geq$ 8x ULN
ALT Increase	ALT $\geq$ 5xULN but $<$ 8xULN persists for $\geq$ 2 weeks ALT $\geq$ 3xULN but $<$ 5xULN persists for $\geq$ 4 weeks
Bilirubina,b	ALT $\geq$ 3xULN and bilirubin $\geq$ 2xULN ( $>$ 35% direct bilirubin)
INRb	ALT $\geq$ 3xULN and INR $>$ 1.5, if INR measured
Cannot monitor	ALT $\geq$ 5xULN but $<$ 8xULN and cannot be monitored weekly for $\geq$ 2 weeks ALT $\geq$ 3xULN but $<$ 5xULN and cannot be monitored weekly for $\geq$ 4 weeks
Symptomaticc	ALT $\geq$ 3xULN associated with symptoms (new or worsening) believed to be related to liver injury or hypersensitivity
Suggested actions and follow-up assessments	
Actions	

Immediately discontinue study medication

Report the event to UCB within 24 hours

Complete the liver event eCRF, and complete an SAE data collection tool if the event also met the criteria for an SAEb

	
Follow-up assessments	

Viral hepatitis serologyd

Obtain INR and recheck with each liver chemistry assessment until the transaminases values show downward trend

Only in those with underlying chronic hepatitis B at study entry (identified by

	

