**Table 10–3: Liver chemistry stopping criteria and follow-up assessments**

Liver chemistry stopping criteria
a Serum bilirubin fractionation should be performed if testing is available. If serum bilirubin fractionation is not immediately available, discontinue study medication if ALT $\geq 3$ xULN and bilirubin $\geq 2$ xULN. Additionally, if serum bilirubin fractionation testing is unavailable, record the absence/presence of detectable urinary bilirubin on dipstick which is indicative of direct bilirubin elevations suggesting liver injury.
b All events of ALT $\geq 3$ xULN and bilirubin $\geq 2$ xULN ( $>35\%$ direct bilirubin) or ALT $\geq 3$ xULN and INR $>1.5$ may indicate severe liver injury (possible ‘Hy’s Law’) and must be reported as an SAE (excluding studies of hepatic impairment or cirrhosis). The INR measurement is not required and the stated threshold value will not apply to participants receiving anticoagulants.
c New or worsening symptoms believed to be related to liver injury (such as fatigue, nausea, vomiting, right upper quadrant pain or tenderness, or jaundice) or hypersensitivity (such as fever, rash or eosinophilia).
d Includes: Hepatitis A IgM antibody; HBsAg and HBCAb; hepatitis C RNA; cytomegalovirus IgM antibody; Epstein-Barr viral capsid antigen IgM antibody (or if unavailable, heterophile antibody or monospot testing); and hepatitis E IgM antibody.
e If hepatitis delta antibody assay cannot be performed, it can be replaced with a PCR of hepatitis delta RNA virus (where needed) (Le Gal et al, 2005).
f Record the date/time of the PK blood sample draw and the date/time of the dose of study medication prior to the PK blood sample draw on the eCRF. If the date or time of the last dose is unclear, provide the participant’s best approximation. If the date/time of the last dose cannot be approximated OR a PK sample cannot be collected in the time period indicated above, do not obtain a PK sample. Instructions for sample handling and shipping are in the Laboratory Manual.

Liver chemistry increased monitoring criteria with continued study medication are presented in [Table 10–4](#).

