Section 5.4.3.1	
Title changed from “AEs of special interest” to “AEs of Special Interest and AEs of Interest”.
 
Definition of AEs of Interest is provided
	Adverse Events (AEs) of hypersensitivity, anaphylactic reactions, drug related hepatic disorders and malignancies or unspecified tumors were added to the AE summaries in order to further assess the ZLP safety and be aligned within the ZLP program.
5.4.3.2.4 Assessment of potential liver toxicity	
Added criterion: AST or ALT >3xULN with INR>1.5 (if INR is measured)
	To define Hy's law according to the study protocol
5.5.1 Pharmacokinetics	
Deleted text:
 
A spaghetti plot of combined individual concentration versus time profiles will be presented by analyte in linear and semi-
	No figures to be created as based on the study protocol PK will be measured in only two timepoints.

	
logarithmic scale with all participants overlaid on the same plot.
 
Additionally, mean (+SD) plasma concentration versus time overlaid for both analytes will also be presented for all scheduled timepoints on a linear and semi-logarithmic scale. The SD will not be provided on the semi-logarithmic scale.
 
All figures will include the LLOQ on the semi-logarithmic plots.
	
5.5.1.4 Participants' treatment satisfaction	
Added text:
 
 Bar charts illustrating the mean and standard error at each visit by domain will be provided. Individual participant listings will be provided for all participants and for participants infected with COVID-19 as per the AE page. 	
 To facilitate the data results interpretation To align with the efficacy questionnaire data
5.7 Interim Analyses	
Added text:
 
“If further interim analysis will be considered during the Main Treatment Period, then this will be of exploratory nature and only descriptive statistics will be provided.”
	Clarification on the analysis purposed of any interim cut during the main treatment period
6.1.1 Baseline characteristics and demographics	
 Deleted text: Additional subgroup summary will be presented based on the enrolled date relative to the cut-off date by during/post COVID-19 pandemic period based on the mITT. An additional cut off of BMI=35 m/kg² is added 	
 Any summaries based on the COVID-19 periods will not be considered. As per UCB updated guidance

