5.4.3.2 Clinical laboratory evaluations

The following table (Table 5.1) lists hematology, chemistry and coagulation analytes that are collected throughout the study, using a central laboratory and following the schedule of assessments according to the protocol.

Table 5.1: Protocol-required safety laboratory assessments

Laboratory assessments	Parameters			
Hematology	Platelet count	RBC indices: MCV MCH %Reticulocytes	WBC count with differential: Neutrophils Lymphocytes Monocytes Eosinophils Basophils	
	RBC count			
	Hemoglobin			
	Hematocrit			
Clinical chemistry ^a	BUN	Potassium	AST/SGOT	Total and direct bilirubin
	Creatinine	Sodium	ALT/SGPT	Total protein
	Glucose	Calcium	Alkaline phosphatase	Amylase
	Lipase			
Routine urinalysis	
• Specific gravity• pH, glucose, protein, blood, ketones, bilirubin, urobilinogen, nitrite, leukocyte esterase by dipstick• Microscopic examination (if blood or protein is abnormal)			
Other screening tests	
• Follicle-stimulating hormone and estradiol (as needed in women of non-childbearing potential only)• Serum hCG pregnancy test (as needed for women of childbearing potential)^b 
The results of each test must be entered into the eCRF.
			

ALT=alanine aminotransferase; AST=aspartate aminotransferase; BUN=blood urea nitrogen; eCRF=electronic Case Report form; HBsAg=hepatitis B surface antigen; hCG=human chorionic gonadotropin; INR=international normalized ratio; IRB=Institutional Review Board; MCH=mean corpuscular hemoglobin; MCV=mean corpuscular volume; RBC=red blood cell; SAE=serious adverse event; SGOT=serum glutamic-oxaloacetic transaminase; SGPT=serum glutamic-pyruvic transaminase; ULN=upper limit of normal; WBC=white blood cell

^a Details of liver chemistry stopping criteria and required actions and follow-up assessments after liver stopping or monitoring event are given in the protocol. All events of ALT $\geq 3 \times$ ULN and bilirubin $\geq 2 \times$ ULN ($>35\%$ direct

Table 5.1: Protocol-required safety laboratory assessments

Laboratory assessments	Parameters
------------------------	------------

bilirubin) or ALT $\geq 3 \times \text{ULN}$ and INR > 1.5 , if INR measured, may indicate severe liver injury (possible Hy's Law) and must be reported as an SAE (excluding studies of hepatic impairment or cirrhosis).

^b Local urine testing will be performed at visits subsequent to the Screening Visit.

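### The SAP's INR criterion for potential drug-induced liver injury (SAP 5.4.3.2.4) leaves out the protocol's exemption for participants on anticoagulants

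*SAP*

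**What the plan says.** SAP 5.4.3.2.4 (Assessment of potential liver toxicity) gives three laboratory criteria for potential drug-induced liver injury. The third is AST or ALT of at least 3×ULN "with INR > 1.5 (if INR is measured"). Its only qualifier is whether an INR exists. Participants with potential drug-induced liver injury are then summarised as a number and percentage. The SAP version history (Amendment 2.0) gives the reason for adding this criterion: "To define Hy's law according to the study protocol".

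Protocol Table 10-3 lists ALT of at least 3×ULN with INR above 1.5 among the liver criteria and attaches footnote b. That footnote ends: "The INR measurement is not required and the stated threshold value will not apply to participants receiving anticoagulants". The same table lists INR among the follow-up assessments once a criterion is met: "Obtain INR and recheck with each liver chemistry assessment until the transaminases values show downward trend".

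Footnote a to protocol Table 10-1, repeated under SAP Table 5.1, also refers to ALT of at least 3×ULN with INR above 1.5 and does not mention anticoagulants. INR is not a listed parameter in either table, although the sentence introducing SAP Table 5.1 says that it "lists hematology, chemistry and coagulation analytes that are collected throughout the study, using a central laboratory".

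**The concern.** The SAP takes over a protocol threshold without the condition that the protocol attaches to it. Anticoagulants are not among the prohibited medications in protocol 6.5.2, and adults up to 85 years are eligible, so a participant on an anticoagulant can be in the study. If that participant has a raised transaminase and an INR is drawn, the SAP table can report a potential liver injury on a threshold that footnote b says does not apply.

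At stake is the agreement between one safety table and the protocol criterion it is meant to reproduce. The trial's primary objective is safety and the sample is about 20, so a single added case is visible. The criterion is also hard to program consistently, because 5.4.3.2.4 does not say which INR results feed it and INR is not on the scheduled panel.

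**Working it through.** The documents give no figure for this point. The check compares the two rules case by case and then sizes one discordant case.

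**Inputs**
- SAP rule (5.4.3.2.4): AST or ALT ≥3×ULN, INR recorded, INR >1.5.
- Protocol rule (Table 10-3 with footnote b): ALT ≥3×ULN, INR recorded, INR >1.5, not on an anticoagulant.
- Planned enrolment: 20 (protocol synopsis; SAP 1.2).
- Number on anticoagulants: not given.

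**Step 1. Classify.** ALT is set at 3.5×ULN for illustration, so that the SAP's wider use of AST plays no part. Every recorded INR is used.

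| On anticoagulant | INR | SAP rule | Protocol rule |
|---|---|---|---|
| No | not measured | not counted | not counted |
| No | 1.2 | not counted | not counted |
| No | 2.5 | counted | counted |
| Yes | not measured | not counted | not counted |
| Yes | 1.2 | not counted | not counted |
| Yes | 2.5 | **counted** | **not counted** |

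Five of the six cases agree. The third row shows that the SAP rule works as intended for a participant who is not on an anticoagulant. Only the last row differs.

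**Step 2. How a participant reaches the last row.** Table 10-3 calls for INR as follow-up after a stopping criterion is met. A raised ALT alone does not always lead there: ALT from 3 to below 8×ULN, without symptoms, with bilirubin below 2×ULN and able to be monitored weekly, falls under Table 10-4, where the repeat tests are ALT, AST, ALP and bilirubin. One route is therefore an anticoagulated participant who meets another Table 10-3 criterion, for example ALT ≥8×ULN, and then has an INR drawn that exceeds 1.5.

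**Step 3. Size.** With a denominator of 20, k discordant participants add 100 × k/20 percentage points. Taking k as an assumption:
- k = 0: 0 points
- k = 1: 100 × 1/20 = 5 points
- k = 2: 100 × 2/20 = 10 points

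A smaller denominator makes each case weigh more. An expected k cannot be derived from the documents.

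**The case against.** The strongest reply is that the SAP list is a screen and not a copy of the stopping rule. It accepts AST as well as ALT, includes a bilirubin level of 1.5×ULN, and drops the direct-bilirubin condition. A participant whose INR was drawn through Table 10-3 already has a qualifying liver event, so calling the case potential is not plainly wrong. The SAP also matches footnote a to protocol Table 10-1, which has no exemption. The output is descriptive, and liver results of participants with elevations are listed, as are medications. A reader of the report could therefore pick out an anticoagulated participant among about 20.

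Most of this stands and limits the weight of the point. It does not remove it. The stated purpose of the criterion was to follow the protocol, and the SAP neither carries the exemption nor explains leaving it out. The agreement with Table 10-1 shows that the protocol states its condition in one place and omits it in another.

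A reader might go further and infer that the criterion can never be met, because SAP 5.4.3.2.1 says "The central data will be used for the summary tables" and INR is not on the central panel. The documents do not support that. The sentence belongs to the section on laboratory values over time. Section 5.4.3.2.4 does not repeat it, presents elevated liver tests at any visit including unscheduled ones, and anticipates an INR that is only sometimes measured. No text says that follow-up INR is a local test. The rule in protocol 8.2.4 beginning "If laboratory values from nonprotocol specified laboratory assessments performed at" covers tests that the protocol does not specify, whereas Table 10-3 does specify this INR.

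**Conclusion.** The omission is confirmed. The SAP rule and footnote b disagree for participants on an anticoagulant who have ALT or AST of at least 3×ULN and a recorded INR above 1.5. Each such participant adds 5 percentage points to a descriptive count, assuming a denominator of 20. The number at risk is unknown and may be zero. This is a minor correction to a safety table; no hypothesis test or decision rule depends on it.

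Two further inferences should not be drawn. One is that every anticoagulated participant with a raised transaminase becomes a false case: the documents do not say that their INR exceeds 1.5, and INR is called for only after a stopping criterion is met. The other is that the table must contradict the serious adverse event reports: the reporting text under Tables 10-1 and 5.1 also lacks the exemption, so the documents do not settle which reports would be made.

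**What to change.** 1. In SAP 5.4.3.2.4, reconcile the third criterion with footnote b as it stands by adding: *excluding participants receiving anticoagulants at the time of the INR*, identified from the concomitant medication data. If the sponsor prefers a broader screen, the SAP should say so and mark anticoagulated participants in the table.
2. Reconcile footnote a to protocol Table 10-1, and its copy under SAP Table 5.1, with footnote b to Table 10-3. These footnotes concern event reporting, so which wording governs is for the sponsor to decide; the point here is only that they differ.
3. State in 5.4.3.2.4 that any recorded INR, including unscheduled or follow-up INR, is used for this criterion, because INR is not a scheduled analyte. Correct the mention of coagulation analytes in the sentence introducing SAP Table 5.1.

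The cost is a clause, a sentence and two footnotes, plus an agreed list of anticoagulant terms for programming. No new data are needed. Pooling local ALT, AST or bilirubin with central results is not needed: protocol Appendix 2 already asks for a central sample alongside any required local one, and pooling could duplicate values.

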### **8.3.6 Adverse events of special interest**

An AE of special interest is any AE that a regulatory authority has mandated to be reported on an expedited basis, regardless of the seriousness, expectedness, or relatedness of the AE to the administration of a UCB product/compound.

For ZLP, the following events require immediate reporting (within 24 hours regardless of seriousness) to UCB:

- Hy's Law
  - Potential Hy's Law, defined as  $\geq 3x$  ULN ALT or AST with coexisting  $\geq 2x$ ULN total bilirubin in the absence of  $\geq 2x$ ULN ALP, with no alternative explanation for the biochemical abnormality (ie, without waiting for any additional etiologic investigations to have been concluded). Follow-up information should be reported if an alternative etiology is identified during investigation and monitoring of the study participant.

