5.4.3.1 AEs of Special Interest and AEs of Interest

The AEs of Special Interest identified in this study are the Hy's Law that are described in Section 5.4.3.2.4.

The following are AEs of Interest (as defined in Section 6.1.6 that require special statistical analyses:

- Hypersensitivity reactions
- Anaphylactic reactions
- Injection site reactions
- Drug related hepatic disorders
- Malignancies or unspecified tumors

The number and percentage of participants who experience each AE of Interest will be summarized separately for each AE of interest. The following summaries will be presented:

- Incidence of AEIs and serious AEIs by SOC and PT (serious and non-serious will appear in the same table)
- Incidence of AEIs by relationship, SOC and PT
- Incidence of AEIs by maximum intensity (mild, moderate and severe), SOC and PT.

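### SAP 5.4.3.2.4 defines potential Hy's Law by a rise in either enzyme, but its same-date sentence asks for both ALT and AST, against the SAP's own definition and protocol 8.3.6

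*SAP*

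**What the plan says.** SAP Section 5.4.3.2.4 treats potential Hy's Law in three consecutive steps.

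- **Definition.** A post-baseline case needs "either AST or ALT" at 3xULN or more, with concurrent ALP below 2xULN and concurrent total bilirubin at 2xULN or more.
- **Same-date sentence.** To meet the criteria, "a study participant must experience the elevation in Bilirubin and ALT and AST (and the absence of the ALP elevation) at the same date".
- **Example.** A participant whose bilirubin is raised on one date and who has an "elevation in ALT (or AST) at a subsequent visit date has not fulfilled" the Hy's Law criteria.

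Protocol Section 8.3.6 defines the same event with "ULN ALT or AST with coexisting" total bilirubin at 2xULN or more, no ALP at 2xULN or more, and no alternative explanation. It places potential Hy's Law under the statement that "the following events require immediate reporting (within 24 hours regardless of seriousness) to UCB".

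SAP Section 5.4.3.1 makes this the only adverse event of special interest and sends the reader to Section 5.4.3.2.4 for its description: "The AEs of Special Interest identified in this study are the" Hy's Law cases. The other topics in that section (hypersensitivity, anaphylaxis, injection site reactions, hepatic disorders, malignancies) are a separate class, AEs of Interest.

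**The concern.** The definition and the sentence that makes it operational cannot both hold. One accepts a rise in either enzyme; the other says a participant must have both. The sentence is worded as a condition for meeting the criteria, so someone programming the flag could reasonably follow it to the letter.

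Two SAP outputs depend on that flag: the number and percentage of participants who potentially meet the Hy's Law criteria, and the graph of each liver test over time, which is produced only for participants who meet them. At stake is whether these two outputs, for the single adverse event of special interest, follow the definition that the SAP and the protocol both state.

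**Working it through.** The documents give no figure on this point, so there is none to reproduce. The check is logical: set the wordings side by side, then list which laboratory patterns each one accepts.

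**Step 1. The wordings**

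| Place | Enzyme condition |
|---|---|
| SAP 5.4.3.2.4, definition | AST or ALT |
| SAP 5.4.3.2.4, same-date sentence | ALT and AST |
| SAP 5.4.3.2.4, example | ALT (or AST) |
| Protocol 8.3.6 | ALT or AST |
| Protocol Table 10-1 and SAP Table 5.1, note a (possible Hy's Law) | ALT, with no condition on AST |

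Only the same-date sentence asks for both enzymes.

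**Step 2. The patterns.** Take four yes/no results on one date: ALT at 3xULN or more, AST at 3xULN or more, total bilirubin (TBL) at 2xULN or more, ALP at 2xULN or more. That gives 2 × 2 × 2 × 2 = 16 combinations. The sentence states no thresholds, so those of the definition are used. The rules are:

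- Protocol 8.3.6 (laboratory part) and the SAP definition: (ALT or AST) and TBL and not ALP.
- SAP same-date sentence: (ALT and AST) and TBL and not ALP.
- SAP potential drug-induced liver injury line: (ALT or AST) and TBL, with no ALP condition.

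Three of the 16 combinations meet protocol 8.3.6. All three have bilirubin raised and ALP not raised:

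| Enzyme at 3xULN or more | Protocol 8.3.6 | SAP definition | SAP same-date sentence | SAP liver injury line |
|---|---|---|---|---|
| ALT only | yes | yes | **no** | yes |
| AST only | yes | yes | **no** | yes |
| Both | yes | yes | yes | yes |

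The sentence keeps 1 of 3 and drops 2 of 3. With *or* in place of *and*, it accepts the same three as the protocol.

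**Step 3. A worked case** (values assumed for illustration). One date: ALT 4.0, AST 2.5, bilirubin 2.2, ALP 1.0 xULN.

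- Definition and protocol 8.3.6: 4.0 ≥ 3, 2.2 ≥ 2 and 1.0 < 2, so the laboratory criteria are met.
- Same-date sentence: AST 2.5 < 3, so not a case.
- Liver injury line: 4.0 ≥ 3 and 2.2 ≥ 2, so counted.

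Exchanging the ALT and AST values gives the same three answers.

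**Step 4. What still shows the dropped participant.** The liver injury line is itself summarized. The SAP also says that "The liver function results for study participants with elevated liver function results will be listed". If ALT is the raised enzyme, the participant also passes both reference lines on the plot of maximum bilirubin against maximum ALT. The Hy's Law count and the per-case graph are what would be lost.

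**The case against.** The best defence is context. The sentence stands between a definition that says either enzyme and an example that says ALT (or AST). Read together, its purpose is to fix timing, and a careful programmer would take it so. The table and listing specifications are in a separate document, so the code cannot be judged from here. This stands as a limit on likelihood: a case is lost only if the sentence is applied literally. It does not remove the contradiction.

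A reader might also infer more than the documents support:

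- **That the same-date rule is itself wrong and needs a time window.** The definition uses *concurrent* for both ALP and bilirubin, and the SAP adds an example on timing, so the choice is deliberate. It is compatible with *coexisting* in protocol 8.3.6, which sets no window. A later rise in bilirubin still qualifies if the enzyme remains at 3xULN or more on that draw. Protocol Tables 10-3 and 10-4 have ALT, AST, ALP and bilirubin repeated together, so each repeat can be judged by the same rule. Neither document gives a basis for any particular window.
- **That a case would vanish and give false reassurance.** Dropped same-date cases remain in the liver injury summary and in the listing.
- **That the reporting of cases is at risk.** The 24-hour report under protocol 8.3.6 does not use the SAP flag.
- **That this sentence would break agreement with the safety database.** Protocol 8.3.6 also requires that there be no alternative explanation, a judgment the laboratory rule does not contain. Flags and reported events need not match one to one in any case.

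**Conclusion.** The point holds as an internal contradiction in one sentence. Read literally, the sentence excludes two of the three same-date patterns that meet the SAP's own definition and the laboratory part of protocol 8.3.6. The effect is confined to the Hy's Law count and the per-case graph; with 20 participants planned, one omitted case would change that percentage by 1/20 = 5 points. Nothing in the documents says how likely such a case is.

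Two assumptions carry this. The first is that the sentence is programmed as written. The second is that the elevation it refers to means the definition's thresholds. If it were taken as any value above ULN, the case with AST at 2.5xULN would pass, and only cases with the second enzyme within normal limits would be dropped; the conflict would be narrower but still there. The matter is minor and worth correcting because the rule concerns the only adverse event of special interest.

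**What to change.** In the same-date sentence of SAP Section 5.4.3.2.4, replace *and* with *or* between ALT and AST. Leave the same-date requirement, the definition and the example as they are. Check that the separate table and listing specifications, and the code for the Hy's Law flag, use the either-enzyme rule.

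The cost is one word in the SAP and a short check of one derivation. No data collection, analysis set or other output changes.
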